12.5.1 Efficacy and/or Pharmacodynamic endpoint(s)

Clinical benefit rate (CBR) is defined as the proportion of participants with a best overall response of complete response (CR) or partial response (PR) or an overall lesion response of stable disease (SD), lasting for a duration of at least 24 weeks. CR, PR and SD are defined as per local review according to RECIST 1.1 (see Section 16.3 Appendix 3 for details). CBR will be evaluated according to RECIST 1.1 (see Section 16.3 Appendix 3 for details).

CBR based on RECIST 1.1 will be calculated based on the FAS and according to the ITT principle. CBR and its two-sided exact binomial 95% confidence interval Clopper CJ and Pearson 1934 will be presented by treatment group.

Time to response (TTR) is defined as the time from the date of randomization to the first documented response of either complete response (CR) or partial response (PR), which must be subsequently confirmed (i.e., the start date of response, not the date when response was confirmed).

TTR will be evaluated according to RECIST 1.1 (see Section 16.3 Appendix 3 for details).

All participants in the FAS will be included in TTR calculations. Participants without a confirmed CR or PR will be censored at the study-maximum follow-up time (i.e., LPLV-FPFV) for participants with a PFS event (i.e., disease progression or death due to any cause), or at the date of the last adequate tumor assessment for participants without a PFS event. TTR will be listed and summarized by treatment group. TTR will be analyzed in the FAS population according to the treatment groups assigned at randomization. The TTR distribution will be estimated using the Kaplan-Meier method, and the Kaplan-Meier curves, medians and 95% confidence intervals of the medians will be presented for each treatment group only if a sufficient number of responses is observed.

Duration of response (DOR) only applies to participants whose best overall response is complete response (CR) or partial response (PR) based on tumor response data per local review. DOR will be evaluated according to RECIST 1.1 (see Section 16.3 Appendix 3 for details).

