Example: In a case where confirmation of response is required the sum of lesion diameters is 200 mm at baseline and then 140 mm - 150 mm - 140 mm - 160 mm - 160 mm at the subsequent visits. Assuming that non-target lesions did not progress, the overall lesion response would be PR - SD - PR - PR - PR. The second assessment with 140 mm confirms the PR for this patient. All subsequent assessments are considered PR even if tumor measurements decrease only by 20% compared to baseline (200 mm to 160 mm) at the following assessments.

If the patient progressed but continues study treatment, further assessments are not considered for the determination of best overall response.

Note: these cases may be described as a separate finding in the CSR but not included in the overall response or disease control rates.

The best overall response for a patient is always calculated, based on the sequence of overall lesion responses. However, the overall lesion response at a given assessment may be provided from different sources:

- Investigator overall lesion response
- Central Blinded Review overall lesion response
- Novartis calculated overall lesion response (based on measurements from either Investigator or Central Review)

The primary analysis of the best overall response will be based on the sequence of investigator/central blinded review/calculated (investigator)/calculated (central) overall lesion responses.

Based on the patients' best overall response during the study, the following rates are then calculated:

Overall response rate (ORR) is the proportion of patients with a best overall response of CR or PR. This is also referred to as 'Objective response rate' in some protocols or publications.

Disease control rate (DCR) is the proportion of patients with a best overall response of CR or PR or SD. The objective of this endpoint is to summarize patients with signs of "activity" defined as either shrinkage of tumor (regardless of duration) or slowing down of tumor growth.

Clinical benefit rate (CBR) is the proportion of patients with a best overall response of CR or PR, or an overall lesion response of SD or Non-CR/Non-PD which lasts for a minimum time duration (with a default of at least 24 weeks in breast cancer studies). This endpoint measures signs of activity taking into account duration of disease stabilization.

Another approach is to summarize the progression rate at a certain time point after baseline. In this case, the following definition is used:

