2.1 Data analysis general information

The primary analysis and final analysis will be performed by Novartis and/or a designated CRO. SAS version 9.3 or later and R version 3.2.3 or later software will be used to perform all data analyses and to generate tables, figures and listings.

Data included in the analysis

The analysis cut-off date for the primary analysis of study data was established after all randomized subjects have been followed for efficacy (tumor assessments) for at least 24 weeks or discontinued tumor assessments for any reason prior to 24 weeks. All statistical analyses will be performed using all data collected in the database up to the data cut-off date. All data with an assessment date or event start date (e.g. vital sign assessment date or start date of an adverse event) prior to or on the cut-off date will be included in the analysis. Any data collected beyond the cut-off date will not be included in the analysis and will not be used for any derivations.

All events with start date before or on the cut-off date and end date after the cut-off date will be reported as ‘ongoing’. The same rule will be applied to events starting before or on the cut-off date and not having documented end date. This approach applies, in particular, to adverse event and concomitant medication reports. For these events, the end date will not be imputed and therefore will not appear in the listings.

The analysis cut-off date for the final analysis of study data will be established at the end of the study, when all subjects have died or discontinued from the study, or another clinical study became available that can continue to provide study treatment in this subject population and all subjects ongoing are eligible to be transferred to that clinical study.

General analysis conventions

Pooling of centers: Unless specified otherwise, data from all study centers will be pooled for the analysis. Due to expected small number of subjects enrolled at centers, no center effect will be assessed.

Qualitative data (e.g., gender, race, etc.) will be summarized by means of contingency tables by treatment arm; a missing category will be included as applicable. Percentages will be calculated using the number of subjects in the relevant population or subgroup as the denominator.

Quantitative data (e.g., age, body weight, etc.) will be summarized by appropriate descriptive statistics (i.e. mean, standard deviation, median, minimum, and maximum) by treatment arm.

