2.5.1 Primary endpoint

The primary endpoint of the study is ORR defined as the proportion of subjects with best overall response (BOR) of complete response (CR) or partial response (PR) according to RECIST 1.1 (see [Appendix 3 of the study protocol](#)). ORR will be calculated based on the FAS using local investigators review of tumor assessment data. Tumor assessments performed before the start of any further antineoplastic therapy (i.e. any additional secondary antineoplastic therapy or surgery) will be considered in the assessment of BOR. Treatment with bisphosphonates or denosumab for pre-existing painful bone metastases and limited-field palliative radiotherapy is permitted as per protocol, and will not be considered as new antineoplastic therapy.

BOR is defined as the best response recorded from the randomization date until disease progression as per RECIST 1.1. Complete and partial responses must be confirmed by repeat assessments that should be performed not less than 4 weeks after the criteria for response are first met.

The BOR for each subject is determined from the sequence of overall (lesion) responses according to the following rules:

CR = at least two determinations of CR at least 4 weeks apart before progression

PR = at least two determinations of PR or better at least 4 weeks apart before progression (and not qualifying for a CR)

SD = at least one SD assessment (or better) > 5 weeks after randomization (and not qualifying for CR or PR).

PD = progression \leq 13 weeks after randomization (and not qualifying for CR, PR or SD).

UNK = all other cases (i.e., not qualifying for confirmed CR or PR and without SD after more than 5 weeks or early progression within the first 13 weeks)

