2.5.3 Handling of missing values/censoring/discontinuations

Subjects with unknown or missing BOR as per RECIST 1.1 will be counted as failures. If there is no baseline tumor assessment, all post-baseline overall lesion responses are expected to be ‘Unknown’. If no valid post-baseline tumor assessments are available, the best overall response must be “Unknown” unless progression is reported. If a complete response is not confirmed, the best overall response must be “Unknown” unless it occurs after the first 5 weeks (stable disease), or confirmed partial response or progression is reported. If a partial response is not confirmed, the best overall response must be “Unknown” unless it occurs after the first 5 weeks (stable disease) or progression is reported. For the computation of ORR, these subjects with unknown BOR will be included in the FAS and will be counted as ‘failures’.

Only tumor assessments performed on or before the start of a new antineoplastic treatment other than study drug(s) (not considering palliative radiotherapy) will be considered in the assessment of BOR.

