Discontinuation due to disease progression (collected on the ‘Treatment disposition’ and ‘Post treatment follow up disposition’ eCRF pages) without supporting objective evidence satisfying progression criteria per RECIST 1.1 will not be considered disease progression for PFS derivation. Clinical deterioration will not be considered as a qualifying event for progression.

Clinical benefit rate (CBR)

CBR is defined as the proportion of subjects with a best overall response (BOR) of confirmed CR or PR, or SD lasting 24 weeks or longer, according to RECIST 1.1 criteria. A subject will be considered to have SD for 24 weeks or longer if a SD response is recorded at (24-1) weeks or later from randomization, allowing for the ± 1 week visit window for tumor assessments. CBR will be calculated using the FAS based on the investigators’ tumor assessments.

Overall Survival (OS)

Overall Survival is defined as the time from date of randomization to date of death due to any cause. All deaths occurring on or before the cut-off date in the FAS will be used in the OS analysis. If a subject is not known to have died, then OS will be censored at the latest date the subject was known to be alive (on or before the cut-off date).

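### Read literally, the CBR timing rule counts SD but not an unconfirmed response at week 23 or later, so a better late scan can turn clinical benefit into none

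*SAP*

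**What the plan says.** SAP 2.7.1 defines CBR as the proportion with a "best overall response (BOR) of confirmed CR or PR, or SD lasting 24 weeks or longer". It then gives a single rule for the duration part: SD is taken to have lasted 24 weeks "if a SD response is recorded at (24-1) weeks or later from randomization". The week taken off allows for the scan window. Protocol 12.5.1 describes the same component as "an overall lesion response of stable disease (SD), lasting for a duration of at least 24 weeks", which is a label attached to a scan.

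The BOR rules are worded differently. SAP 2.5.1 has "SD = at least one SD assessment (or better) > 5 weeks after randomization". SAP 2.5.3 says that a participant with an unconfirmed PR has an unknown BOR "unless it occurs after the first 5 weeks (stable disease) or progression is reported". Confirmation requires a repeat assessment "performed not less than 4 weeks after the criteria for response are first met".

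At scan level, a PR that is not yet confirmed keeps the label PR. In the worked example in Protocol 16.3.3.1, for a study that requires confirmation, "the overall lesion response would be PR - SD - PR - PR - PR".

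The primary analysis was timed for when all participants had been "followed for efficacy (tumor assessments) for at least 24 weeks", or had stopped tumor assessments earlier. SAP 2.1 excludes data collected after the cut-off.

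**The concern.** The two sets of rules do not meet. BOR treats an unconfirmed late PR as stable disease. The CBR timing sentence then looks for a scan labelled SD at week 23 or later, and a scan labelled PR does not satisfy it. A participant can therefore have a BOR of SD, be free of progression at week 24 with a shrinking tumor, and still fail the 24-week test, although an unchanged scan on the same day would have passed.

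Two things are at stake. The rule can rank a better scan below a worse one, which does not fit the stated purpose of CBR in Protocol 16.3.3.1 (activity that takes account of how long the disease is stabilized). Also, two competent programmers could derive different CBRs from the same data, depending on whether they carry the BOR convention over.

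**Working it through.** The documents give no CBR figure, so there is nothing to reproduce. The check applies the rules to scan sequences.

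**Inputs**
- Scans every 6 weeks, ±7 days, for the first 9 months (Protocol 8.3.1): weeks 6, 12, 18, 24, 30, 36.
- BOR rules from SAP 2.5.1 and 2.5.3, with a confirmation interval of at least 4 weeks.
- CBR rule from SAP 2.7.1, with the threshold at week 24 − 1 = 23, i.e. 23 × 7 = 161 days.
- Arm sizes 20, 34 and 34, and a primary cut-off of 27-Feb-2020 (Protocol, Amendment 4).
- 19, 21 and 21 randomized in Arms 1, 2 and 3 at Amendment 3, dated 28-Mar-2019 (Protocol, Amendment 3).

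**Classification.** Every sequence starts with SD at weeks 6, 12 and 18.

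| Week 24 | Week 30 | BOR | CBR, rule as written | CBR, SD or better |
|---|---|---|---|---|
| SD | none, UNK, PD, SD or PR | SD | yes | yes |
| PR | none | SD | **no** | yes |
| PR | UNK | SD | **no** | yes |
| PR | PD | SD | **no** | yes |
| PR | SD | SD | yes | yes |
| PR | PR | PR (confirmed) | yes | yes |

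SD-SD-SD-SD-PD counts as benefit and SD-SD-SD-PR-PD does not, although BOR is SD in both. Starting new therapy or reaching the cut-off after the week-24 PR has the same effect as having no week-30 scan. A single late CR behaves like a single late PR.

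The response at week 23 or later has to be the first one. Had an earlier PR been recorded at least 4 weeks before, the later PR would confirm it and the participant would count as a responder.

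**Size per case.** Shift in CBR = 1/n: 1/34 = 2.9 percentage points in Arms 2 and 3, and 1/20 = 5.0 in Arm 1. With k cases the shift is k/n. The documents do not give k, and k = 0 is possible. As an illustration with assumed counts, 12/34 = 35.3% (exact 95% CI 19.7 to 53.5) becomes 13/34 = 38.2% (22.2 to 56.4) with one reclassification.

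**Who could be caught by the cut-off.** From 28-Mar-2019 to 27-Feb-2020 is 336 days, or 336/7 = 48 weeks. The 19 Arm 1 participants and the 21 in each of Arms 2 and 3 already randomized by then had at least 48 weeks before the cut-off, which leaves room for the week-30 and week-36 scans after a week-24 PR. Those randomized later number 20 − 19 = 1 in Arm 1 and 34 − 21 = 13 in each of Arms 2 and 3. Only those among them enrolled near the end could have a week-24 PR as their last usable scan.

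**The case against.** The strongest reply is that SD in the CBR definition means the BOR category. SAP 2.7.1 introduces CBR through BOR, SAP 2.5.1 lets SD or better qualify as SD, and SAP 2.5.3 calls an unconfirmed PR after week 5 stable disease. Protocol 16.3.3.2.6 adds a duration of stable disease that covers CR, PR and SD and runs to progression, so that a PR scan would not end it. On that reading the late PR counts and nothing is lost.

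This probably shows what was intended, and it makes an omission more likely than a deliberate exclusion. It does not settle the text. The timing sentence asks for a recorded SD, Protocol 12.5.1 ties the component to the overall lesion response, and the worked example labels the unconfirmed scan PR. The duration in Protocol 16.3.3.2.6 is offered only as an optional extra for large Phase III studies. No passage says that an unconfirmed response meets the week-23 test.

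Other parts of the reply stand. Protocol 8.3.1 requires a confirmatory scan after a first response, which narrows the affected group. Delayed effect is treated only as a contingency: SAP 2.5.4 allows an optional analysis counting unconfirmed responses, and that analysis is for ORR, not CBR. CBR has no test or decision rule attached. And the primary analysis is done, so a wording change now comes after the data have been seen.

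**Conclusion.** The rule as written misclassifies a narrow group: BOR of SD, first PR or CR at week 23 or later, never confirmed, and no SD scan from week 23 on. Relative to an SD-or-better rule the error can only lower CBR, by 2.9 points per case in Arms 2 and 3 and 5.0 in Arm 1. This assumes that the rule was programmed literally, which the documents do not show. The point is minor: the endpoint is secondary and descriptive, and proof of preliminary efficacy rests on confirmed ORR.

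A reader might infer three stronger things.
- That every unconfirmed week-24 PR is counted as no benefit. It is not: a later SD scan satisfies the rule.
- That the 24-week minimum follow-up makes the loss systematic. The dates do not support this. Cut-off truncation cannot explain cases among 19 of the 20 Arm 1 participants or 21 of the 34 in each other arm, and it is plausible mainly for late-enrolled Arm 2 and 3 participants.
- That the reported CBR is shown to be biased. No number of affected participants can be derived from the documents, and it may be zero.

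**What to change.** In SAP 2.7.1, replace the reference to an SD response by an overall lesion response of SD or better, keep the week-23 threshold, and add that the scan must come before progression and before new antineoplastic therapy. The therapy limit matches the one for BOR in SAP 2.5.3; the CBR sentence currently states neither limit. With this wording all ten sequences above count as benefit.

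Because the primary analysis has been reported on, first check how CBR was programmed. If unconfirmed late responses were already treated as SD, the change only documents what was done. If not, list the participants who meet the conditions above, footnote any whose classification changes with CBR under both readings, and note the clarification in SAP section 4, which now reports no change to the protocol-specified analyses. The cost is a few words and one derivation check, plus a footnote if anyone moves.

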2.7.2 Statistical hypothesis, model, and method of analysis

Duration of response

DOR based on RECIST 1.1 will be listed and summarized by treatment group for all subjects in the FAS with confirmed BOR of CR or PR. DoR will be analyzed in the FAS population according to the treatment groups assigned at randomization. The DoR distribution will be estimated using the Kaplan-Meier method, and the Kaplan-Meier curves, medians and 95% confidence intervals of the medians [[Brookmeyer and Crowley 1982](#)] will be presented for each treatment group only if a sufficient number of responses is observed. DoR will also be summarized for the subgroups specified in [Section 2.2.1](#).

Time to response

TTR will be listed and summarized by treatment group. TTR will be analyzed in the FAS population according to the treatment groups assigned at randomization. The TTR distribution will be estimated using the Kaplan-Meier method, and the Kaplan-Meier curves, medians and 95% confidence intervals of the medians [[Brookmeyer and Crowley 1982](#)] will be presented for each treatment group only if a sufficient number of responses is observed. A responders-only analysis will also be performed in this case.

Progression-Free Survival

PFS will be analyzed in the FAS population according to the treatment group assigned at randomization and including all data observed up to the cut-off date. The survival distribution

of PFS will be estimated using the Kaplan-Meier method. The results will be plotted graphically by treatment arm using Kaplan-Meier curves. The medians of PFS and 95% confidence intervals of the medians [Brookmeyer and Crowley 1982], along with the proportion of subjects event-free at 3, 6, 12 and 18 months and the associated 95% confidence intervals, will be presented for each treatment group.

Censoring pattern of PFS

Number of subjects with a PFS event and number of subjects censored for the PFS analysis will be summarized. In addition, a summary of reasons for PFS censoring will be provided by treatment arm based on the following reasons:

- 1: Ongoing without event
- 2: Lost to follow-up
- 3: Withdrew consent
- 4: Adequate assessment no longer available
- 5: Initiation of new cancer therapy prior to progression
- 6: Event after ≥ 2 missing tumor assessments

The PFS censoring reasons are defined in the following way.

If the time interval between the last adequate tumor assessment (TA) date and the earliest of the following dates is smaller or equal to interval of 2 missing tumor assessments:

1. Analysis cut-off date,
2. Start date of further anti-neoplastic therapy,
3. Date of consent withdrawal,
4. Visit date of study treatment discontinuation or end of post-treatment follow-up discontinuation due to lost to follow-up.

Then the PFS censoring reason will be:

1. 'Ongoing',
2. 'New cancer therapy added',
3. 'Withdrew consent',
4. 'Lost to follow-up',

If the time interval is larger than the interval of 2 missing tumor assessments with no event observed. then the PFS censoring reason will always default to 'Adequate assessment no longer available'. If the time interval between the last adequate tumor assessment date and the PFS event date is larger than the interval of 2 missing tumor assessments then the subject will be censored and the censoring reason will be 'Event documented after two or more missing tumor assessments'.

These summaries on censoring reasons will be produced for PFS by investigators' assessment. The censoring patterns will be compared between treatment arms.

As a supportive analysis, the same type of analysis will be done for PFS, without censoring the data of tumor assessments after the start a the new anticancer therapy.

Clinical benefit rate

CBR based on RECIST 1.1 will be calculated based on the FAS and according to the ITT principle. CBR and its two-sided exact binomial 95% confidence interval [[Clopper and Pearson 1934](#)] will be presented by treatment group.

Overall Survival

OS will be analyzed in the FAS population according to the treatment group assigned at randomization and including all data observed up to the cut-off date. The survival distribution of OS will be estimated using the Kaplan-Meier method. The medians of OS and 95% confidence intervals of the medians [[Brookmeyer and Crowley 1982](#)], along with the proportion of subjects alive at 3, 6, 12 and 18 months and the associated 95% confidence intervals, will be presented for each treatment group.

Censoring pattern of OS

The pattern of censored data will be examined between the treatment arms: reasons for censoring ('Alive' or 'Lost to follow-up') and death cause will be summarized by treatment arm. In addition, survival status, reason for censoring and death cause will be listed. Subjects not known to have died will be censored for 'Lost to follow-up' if the time between their last contact date and the analysis cut-off date is longer than the protocol specified interval between the survival follow-up assessments plus 2 weeks, i.e., 15 weeks for this study.

Duration of follow-up for PFS/OS

Study follow-up will be summarized using the following methods: summary of duration between randomization and cut-off date, and follow-up times for PFS/OS, which are defined as follows:

- Duration between randomization and data cut-off date = (Cut-off date – Date of randomization + 1) / 30.4375 (months). This item will be summarized overall.
- Follow-up time = (Date of event or censoring – Date of randomization + 1) / 30.4375 (months) regardless of censoring. Date of censoring is defined as the last adequate tumor assessment date for PFS or last contact date for OS. This item will be summarized by treatment arm.

All summaries will be reported in months. Date of censoring is the same as defined for the PFS and OS analysis.

In addition, median time to censoring will be computed by reversing censoring variable and performing Kaplan-Meier analysis.

